12.9.2.6 Comparison of Days in Hospital, ICU and Ventilation

Cumulative number of days for Hospitalization, ICU and Intubation / Mechanical Ventilation will be compared across treatment groups using non-parametric Wilcoxon Rank Sum test. The test will be two-sided with level of significance of 5%. Descriptive summaries of cumulative number of days,

difference in treatment groups, 95% CI and unadjusted p-value will be reported. P-value will be from testing the null hypothesis that mean of cumulative days across treatment groups are same.

Reference SAS Program:

```
proc npar1way data=<data>;
  class <treatment>;
  var <days>;
run;
```

In DDP: Table 14.2.6.3 and Table 14.2.6.4

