#### **Number of subjects (enrolled):**

Part 1: A total of 60 evaluable participants randomized 1:1 to rhu-pGSN:placebo (30:30 subjects).

Part 2: A total of 20 evaluable participants randomized 1:1 to rhu-pGSN:placebo (10:10 subjects).

Although data will be examined both in total as well as grouped by baseline WHO score, subjects will not be formally stratified by severity group.

All reported deaths and treatment-emergent SAEs will be evaluated by the Data and Safety Monitoring Board (DSMB) within 4 working days of notification of the Contract Research Organization (CRO)/Sponsor.

In Part 1, periodic safety reviews will be conducted after 12, 24, 36, and 48 subjects have been fully dosed and completed assessment at Day 14. Only DSMB members will be provided with partially unblinded results separated into 2 groups by treatment without identifying the actual treatment. If all participants have completed study therapy before the last DSMB meeting involving review of 48 subjects after their Day 14 visit can be held, this meeting can be cancelled at the discretion of the DSMB chair. Data will be further unblinded and/or the study paused at the discretion of the DSMB chair; enrollment will continue during the safety analyses unless otherwise mandated by the DSMB chair.

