## 11. STATISTICS

### 11.1. General Overview

All subjects given e 1 dose of study drug will be included in the Full Analysis Set (FAS) according to actual drug received; non-completers will be counted as failures in the primary efficacy analysis. Subjects receiving all 3 doses and evaluable for the primary Day 14 endpoint will constitute the per-protocol population for efficacy assessment. WHO severity score will be recorded daily while the subject is hospitalized, after discharge through Day 14, where feasible, and at each follow-up visit.

AE data will be summarized for the FAS by actual drug received using counts and proportions of subjects having an AE, each AE type, and an AE of each System Organ Class. SAEs and reasons for any early discontinuation will be summarized similarly. All deaths will be categorized by cause of death as per investigator assessment and relationship to study drug and/or COVID-19

Immunogenicity will be assessed on Days 1(predose), 28, and 90 days in all participants. Antibodies against pGSN will be assayed from frozen specimens to determine whether the investigational product induces an antibody response in recipients.

For Part 1, binary efficacy endpoints will be compared between treatments via stratified Cochran-Mantel-Haenszel (CMH) test and, to accommodate continuous covariates, via logistic regression. Continuous efficacy and biochemical endpoints will be compared between treatments via mixed model repeated measures analysis or analysis of covariance, depending on whether repeated measures are available or not. Time-to-event analysis via stratified log rank test and Cox proportional hazards model may also be carried out as supplemental analyses.

For Part 1, exploratory analyses looking at biomarkers and outcomes in each treatment arm will be conducted. Other exploratory analysis to compare the efficacy endpoint data from the rhu-pGSN group from this study to that of external control data may be carried out if appropriate. Sample size may be increased to improve the precision of the estimates of between-treatment comparisons if appropriate and if drug supplies are available.

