## **11.2. Sample Size and Power Calculations**

The primary endpoint is difference between treatments in the proportion of surviving subjects off vasopressors, the ventilator, and dialysis on Day 14. For Part 1, the power for the study is computed for the expected increase in proportion of surviving subjects without these supports at Day 14 after start of study treatment. A total sample size of N=54 has ~80% power to yield a statistically significant (alpha=0.2 1-sided) difference if the TRUE underlying proportions are 20% and 5% for placebo plus SOC and rhu-pGSN plus SOC, respectively. The minimum OBSERVED difference from placebo plus SOC proportion 20% that yields statistical significance is 8.4% (20% vs 11.6%). As this is a pilot Phase 2 POC trial in an infection with no approved therapy and false negative error (100% minus power) is equally as important as false positive error, the one-sided type 1 error is set at 0.2. Thus, the trial is adequately powered for its primary POC objective.

For Part 2, a sample size of 20 subjects was chosen to generate an estimate of any clinically relevant treatment effect.

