12.9.2.2 Time to Death (Days)

12.9.2.2.1 Log-Rank Test

Time-to-event statistics including number of subjects with event (see section 11.18), censored, mean, standard error, median time along with 95% CI, 25th and 75th quartiles, minimum and maximum will be reported in a summary table. Log Rank test will be performed to compare the survival probability curves between treatment groups and corresponding unadjusted p-values will be included.

Percentage of subjects alive at Day 28 and Day 90 will be estimated using Kaplan-Meier method. 95% CI for the point estimate will also be presented.

Reference SAS Program:

```
proc lifetest data =  plots=survival;
  time <duration>*<censor> (1);
  strata <treatment>/ test=LOGRANK;
run;
```

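### Hospital, ICU and ventilator days are tested without the covariance adjustment the protocol planned, and the SAP does not record the change

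*SAP*

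**What the plan says.** **Protocol 11.1**, for Part 1: "Continuous efficacy and biochemical endpoints will be compared between treatments via mixed model repeated measures analysis or analysis of covariance", the choice depending on whether there are repeated measures. Cumulative days give one value per subject, so the planned method is analysis of covariance. No covariate is named.

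**SAP 12.9.2.6**: the days "will be compared across treatment groups using non-parametric Wilcoxon Rank Sum test", two-sided at 5%. The reference code has treatment as the class variable and days as the response, and the p-value is described as unadjusted.

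**SAP 16.1** shows no supportive analysis for ventilator days or for hospital and ICU days. For hospital and ICU days it lists descriptive summaries only, which does not match the test in 12.9.2.6.

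**SAP section 13** records two changes: the WHO-score visits and the external-control comparison. It says nothing about this one.

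**Baseline WHO score.** The protocol synopsis says data will also be examined by baseline WHO score, but "subjects will not be formally stratified by severity group". The SAP puts the score in the MMRM (12.9.2.1.3) and the Cox model (12.9.2.2.2), and treats it as the stratification factor in a secondary CMH analysis (12.9.2.3.1).

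**The concern.** Part 1 subjects enter with WHO scores from 4 (oxygen by mask or nasal) to 6 (which includes intubation). Among these scores only 6 includes intubation, so only those subjects can already be accruing ventilator days at entry. It is plausible that entry severity also affects ICU and hospital days.

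An unadjusted test leaves that variation in the error term. With 30 per arm and no stratification by severity, it also leaves any chance imbalance uncorrected. A real reduction in days could be missed, or an imbalance could be read as a drug effect. An adjustment chosen after the imbalance is seen would be post hoc.

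There is also a question of record: a reader of section 13 would not learn that the planned method was replaced.

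**Working it through.** **1. The plan's own power figure.** It concerns the primary endpoint: "A total sample size of N=54 has ~80% power" for a "statistically significant (alpha=0.2 1-sided) difference" when the "TRUE underlying proportions are 20% and 5% for placebo plus SOC and rhu-pGSN plus SOC" respectively. With 27 per arm and pooled variance under the null:

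- mean proportion = (0.20 + 0.05)/2 = 0.125
- null term = √(2 × 0.125 × 0.875) = 0.4677
- alternative term = √(0.20 × 0.80 + 0.05 × 0.95) = 0.4555
- power = Φ[(0.15 × √27 − 0.8416 × 0.4677)/0.4555] = Φ(0.847) = 80.1%

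The figure reproduces. The documents state no power for the days endpoints, so the effect on days and its correlation with WHO score are assumptions below.

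**2. Approximate size of the loss.** Inputs: 30 per arm (protocol 7.1), two-sided 5% (SAP 12.9.2.6), rank-sum efficiency 3/π, an effect of d standard deviations (assumed), and a share R² of variance explained by WHO score (assumed).

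- Rank-sum: Φ(d√(15 × 3/π) − 1.96). At d = 0.74: Φ(2.80 − 1.96) = 80%.
- Adjusted: divide the first term by √(1 − R²). R² = 0.10 gives Φ(2.95 − 1.96) = 84%. R² = 0.30 gives Φ(3.35 − 1.96) = 92%.

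This ignores the cost of ranking within small strata, so simulation is needed.

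**3. Simulation, log-normal days.** 60 subjects 1:1, WHO 4/5/6 in equal thirds, 6,000 runs per row, effect 0.74 SD.

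| R² | Rank-sum | Van Elteren | Rank ANCOVA |
|---|---|---|---|
| 0 | 79.8% | 76.7% | 79.3% |
| 0.1 | 77.7% | 79.8% | 81.3% |
| 0.2 | 78.1% | 84.3% | 86.1% |
| 0.3 | 77.1% | 88.5% | 89.4% |
| 0.4 | 77.5% | 93.0% | 93.6% |

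A 60/30/10 mix gives similar figures. A second simulation (3,000 runs per setting, effects of 0.6 and 0.75 SD) is set by correlation:

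| Correlation | Rank-sum to van Elteren, 0.6 SD | Same, 0.75 SD |
|---|---|---|
| 0.3 | 59.8% to 61.1% | 79.0% to 80.1% |
| 0.5 | 60.5% to 69.9% | 78.7% to 86.6% |
| 0.6 | 60.3% to 77.5% | 78.3% to 91.8% |

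With no drug effect, the rejection rates lay between 4.2% and 6.1% across the two simulations, so the plain test keeps its size on average.

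**4. Ventilator days that are mostly zero.** Log-normal days for everyone does not describe an endpoint that many subjects never reach. Assumed: 12% to 32% of placebo subjects ventilated; risks by WHO 4/5/6 of 5/20/50, 10/20/40, 10/25/60 or 20/20/20%; odds ratio 0.21 or 0.4, with shorter stays on drug; WHO mixes 33/33/33, 60/25/15 and 75/15/10. Van Elteren minus rank-sum ran from −3 to +7 points, and from −3 to +4 in the two mixes with most subjects at score 4. The gain becomes large only if nearly all WHO 6 subjects are ventilated. ICU days may behave in the same way.

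**5. A chance imbalance.** Take log-normal days, correlation 0.5, an effect of 0.75 SD, and WHO 4/5/6 counts of 7/10/13 on drug and 13/10/7 on placebo. The mean scores are 156/30 = 5.2 and 144/30 = 4.8, a difference of 0.4.

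- With a drug effect: rank-sum power falls from about 81% (balanced arms) to 45%; van Elteren has 86%.
- With no drug effect: the rank-sum test rejects 11.6% of the time, all toward harm; van Elteren rejects 5.4%. The mirror imbalance would give false benefit.
- With 20 subjects at each score, a difference of 0.4 or more in either direction has roughly an 8% chance.

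**The case against.** The strongest case for the SAP is this. A rank test suits skewed, tied day counts, and it is valid. The endpoints are secondary, no power target is set for them, and SAP 8.2 already asks for caution in reading secondary tests. The protocol names no covariate, so WHO score is an inference. WHO levels 5 and 6 also overlap as worded (high-flow oxygen, and oxygen by high-flow nasal goggles), which could weaken the score as a predictor. Van Elteren is not analysis of covariance either.

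Most of this stands, and it limits the point to efficiency, protection against imbalance, and an unrecorded change. It does not remove the point: the SAP already relies on baseline WHO score in three other analyses, and these endpoints have no adjusted analysis at all.

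A reader might also infer that the mortality comparison has the same fault, because SAP 12.9.2.2.1 says a "Log Rank test will be performed to compare the survival probability curves between treatment groups" and its code has no WHO stratum. The documents do not support that. The protocol's wording is optional, "Time-to-event analysis via stratified log rank test and Cox proportional hazards model may also be carried out as supplemental analyses", and it names no stratum. SAP 12.9.2.2.2 reports a WHO-adjusted Cox hazard ratio in the same table. Stratifying would also gain little with few deaths: at 10% to 20% placebo mortality, power changed by about −3 to +3 points.

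**Conclusion.** The point holds for hospital, ICU and ventilator days. The test departs from protocol 11.1, the departure is not in SAP section 13, and no adjusted analysis is planned.

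Van Elteren changes power by about −3 to −2 points if WHO score is unrelated to days, +1 to +2 at correlation 0.3 and +8 to +10 at 0.5. These figures assume log-normal days and 30 per arm, and the documents give neither the correlation nor the effect. They fit hospital days best. For ventilator or ICU days that are mostly zero, −3 to +7 points is more realistic, so the larger gain should not be quoted for all three endpoints.

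A reader might infer that the unadjusted p-values are invalid. They are not: size averages about 5% over allocations. The weakness appears when a particular allocation is unbalanced in severity. Nor does the protocol itself require WHO score as the covariate; that choice rests on how the SAP treats its other endpoints. The primary endpoint and its power are unaffected.

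**What to change.** - In SAP 12.9.2.6, make the main comparison a rank-sum test stratified by baseline WHO score (van Elteren: `tables bsl_who*treatment*days / cmh2 scores=modridit` in PROC FREQ), or rank ANCOVA with baseline WHO score.
- State in advance that a sparse WHO level is pooled with its neighbour, since a level with only one arm contributes nothing to a stratified test.
- Keep the plain rank-sum test as supportive.
- Record the departure from analysis of covariance in section 13, and bring the hospital and ICU row of 16.1 into line with 12.9.2.6.

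The cost is wording and a few lines of code, with no new data. The downside is a loss of 2 to 3 points of power with van Elteren if WHO score is not prognostic (0.5 point with rank ANCOVA in the equal-thirds simulation), plus the pooling rule. The log-rank test for death needs no change on this account.

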12.9.3 Other Analyses

12.9.3.1 Arterial Blood Gas Test

Descriptive summary of absolute results and change from baseline for Arterial blood gas test parameters in baseline and post-baseline visits will be summarized by treatment groups. The parameters to be summarized are, pH, pCO₂, pO₂, %O₂ and cmH₂O. The summary will be presented for FAS and per-protocol analysis set.

In DDP: Tables 14.2.7.1 and 14.2.7.2

Absolute results change from baseline, etc. for all parameters will be listed by subject and grouped by treatment and visit.

In DDP: Listing 16.2.6.6

12.9.3.2 Hypotension requiring treatment beyond fluids (Vasopressors)

Number and percentage of subjects who have taken any vasopressors will be summarized by treatment. The same will be classified by Therapeutic Main group (ATC Level 2) and Chemical Subgroup (ATC Level 4). If ATC level 4 is missing, ATC levels 2 or 3 will be used. The therapeutic main group and chemical subgroup will be displayed in the descending order of frequency in "Total". Medications will be coded using the World Health Organization's Drug-Dictionary (WHODrug) version September 2020 or latest.

The summary will be presented for FAS and per-protocol analysis set. Percentages will be based on corresponding analysis sets.

In DDP: Tables 14.2.8.1 and 14.2.8.2

All medications will be listed by subject and therapeutic subgroup. Subjects will be grouped by treatment.

In DDP: Listing 16.2.6.7

12.9.3.3 CURB-65 Score

Shift in CURB-65 scores from baseline (scores 1-5) to each post-baseline visit (Days 3, 7, 14, 28 and 60) will be presented by treatment groups. Subjects whose values are missing or assessment is not done will be presented as 'Missing / Not Done'.

The summary will be presented for FAS and per-protocol analysis set. Percentages will be based on corresponding analysis sets.

In DDP: Tables 14.2.9.1 and 14.2.9.2

CURB-65 scores will be listed by subject and grouped by treatment groups and visits.

In DDP: Listing 16.2.6.8

12.9.3.4 Abbreviated Mental Health Score

Descriptive summaries for the total score and change from baseline to post-baseline visits will be summarized by treatment groups. The summary will be based on FAS and per-protocol analysis set. Percentages will be based on the corresponding analysis sets.

In DDP: Tables 14.2.10.1 and 14.2.10.2

Abbreviated mental health scores will be listed by subjects.

In DDP: Listing 16.2.6.9

12.9.3.5 Sputum Microbiology, Blood cultures and Dialysis

Sputum microbiology, Blood cultures and Dialysis/RRT data will only be listed by subject.

In DDP: Listing 16.2.6.11, 16.2.6.12 and 16.2.6.5

12.9.3.6 Confirmation of COVID-19 pneumonia

Confirmation of COVID-19 pneumonia by RT-PCR, CXR scan radiologic findings, and CT scan radiologic findings will be listed by subject.

Note: Subject who have screening COVID-19 confirmation before Informed Consent Date will be discussed during the Blinded Review Meeting prior to DB Lock.

In DDP: Listing 16.2.6.10

12.9.4 Pharmacodynamic Parameters

Descriptive summary of parameters for baseline, each post baseline visit, and change from baseline at each visit and time point will be presented by treatment group. The summary will be based on FAS analysis set. The decision on whether biomarker results will be analyzed, and list of biomarkers to be analyzed will be made after database lock.

All PD parameters will be listed for FAS analysis set.

In DDP: Table 14.4.1.1 And Listing 16.2.10.1

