#### **11.4.4. Pharmacodynamics**

Biomarker and clinical outcomes will be summarized via counts and percentages of subjects for categorical variables, and by summary statistics (N, mean, median, standard deviation, minimum, maximum, 90% confidence intervals, etc.) for baseline, each observed time point, and change from baseline at each observed time point for continuous variables. Data will be assessed via graphical and Shapiro-Wilk statistic for closeness to normal distribution and if substantial departure is observed, transformation (e.g., natural log, reciprocal, square root, ranks) may be employed to derive the summary statistics.

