8.1 General Conventions

All analyses will be done using SAS (version 9.4, SAS Institute Inc., Cary, NC, USA).

Efficacy and Safety endpoints will be analyzed in a descriptive manner. Continuous data will be reported using the following descriptive statistics:

1. Number of observations (n)
2. Mean and Standard deviation (SD)
3. Interquartile Range (IQR)
4. Minimum (min) and Maximum (max)
5. Median

In addition:

6. Geometric mean & Standard deviation
7. Coefficient of variation (CV%)
8. Geometric CV%

will be reported for plasma concentration data and PK parameters. Categorical data will be presented using frequency (n = number of subjects; m = number of events) and percentage (%).

Listings will be provided for all data recorded in eCRF to study subject profiles. All listings will be sorted by treatment, subject ID, and date (if applicable). Unscheduled visit data will only be listed and not included in summaries.

All p-values will be displayed to four decimal places, with p-values less than 0.0001 presented as '<0.0001' and p-values greater than 0.9999 presented as '>0.9999'. Minimum and maximum values will be reported in the units of collection with 3 decimals being maximum value; the mean will be presented with 1 decimal place more and the standard deviation 2 decimal places more than the units of collection. Percentages for categorical summaries will be represented to 1 decimal place.

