11.7.1 Change from Baseline

Change between Baseline and post-baseline result will be calculated as:

Change from baseline = Result at Visit X – Baseline Result

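### The SAP gives biomarkers only descriptive summaries by arm, without declaring that it omits the protocol's between-arm comparison and normality check, and it leaves the marker list open until after database lock

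*SAP*

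**What the plan says.** **Protocol.** Section 11.1 states for Part 1: "Continuous efficacy and biochemical endpoints will be compared between treatments via mixed model repeated measures analysis or analysis of covariance", the choice depending on whether repeated measures exist. Section 11.4.4 (Pharmacodynamics) is a summary section: "Biomarker and clinical outcomes will be summarized via counts and percentages of subjects for categorical variables, and by summary statistics". It then adds a check, "Data will be assessed via graphical and Shapiro-Wilk statistic for closeness to normal distribution", and says that on substantial departure a "transformation (e.g., natural log, reciprocal, square root, ranks) may be employed to derive the summary statistics". Section 5.2.3 lists change in biomarkers over time with treatment as an exploratory endpoint. Table 5 schedules biomarker sampling on Days 1, 3, 7, 14, 28 and 60. Section 9.4 names ferritin, D-dimer, CRP and procalcitonin (local laboratory), with cytokines from stored aliquots.

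**SAP.** Section 12.9.4, on the FAS and split by arm, reads: "Descriptive summary of parameters for baseline, each post baseline visit, and change from baseline at each visit and time point will be presented". Section 11.7.1 defines change arithmetically: "Change from baseline = Result at Visit X – Baseline Result". Section 8.1 lists n, mean, SD, IQR, minimum, maximum and median for all continuous data. Geometric mean, CV% and geometric CV% "will be reported for plasma concentration data and PK parameters". The biomarker row of 16.1 shows descriptive summaries and no supportive analysis. Sections 12.9.4 and 12.10.5 both defer the decision on whether biomarkers are analysed, and which, until after database lock. Section 13 declares two changes, the timing of the WHO score and the dropped external-control comparison. Neither concerns biomarkers.

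**The concern.** The protocol's rationale (section 4.5) is that the drug tempers an excessive inflammatory response. Biomarker change by arm is the natural supporting evidence for that. Followed as written, the SAP yields two columns of summaries and no estimate of the difference between them.

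A reader will then compare the columns by eye. With about 30 subjects per arm, that comparison carries chance baseline imbalance. If the markers are right-skewed, the mean changes also depend heavily on a few subjects with very high values.

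No method, scale or marker list is fixed before lock. Any contrast added later would therefore be chosen after the fact, possibly with treatment allocation known.

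**Working it through.** **1. The documents side by side.**

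| Element | Protocol | SAP |
|---|---|---|
| Between-arm comparison | MMRM or ANCOVA, firm (11.1) | None for biomarkers (12.9.4, 16.1); MMRM only for the WHO score (12.9.2.1.3) |
| Normality check | Firm (11.4.4) | Absent |
| Transformation | Permitted on substantial departure (11.4.4) | Absent; geometric statistics for PK only (8.1) |
| Change declared | n/a | Not in section 13 |

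The safety laboratory tables (SAP 12.10.3) also list ferritin, D-dimer, CRP and procalcitonin, but these too are descriptive.

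**2. The plan's own figure.** The documents give no biomarker SD, correlation or power. The only sample-size figure is for the primary endpoint: N=54, 20% vs 5%, one-sided alpha 0.2. It reproduces at 80.1% power with 27 per arm. It has no bearing on this point beyond supplying n = 27.

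**3. What baseline adjustment is worth.** Assume equal SD at baseline and visit, with correlation r. The variance of a change score is 2(1-r)SD²; after ANCOVA it is (1-r²)SD². The ratio is 2/(1+r).
- r = 0.3: 1.40/0.91 = 1.54
- r = 0.5: 1.00/0.75 = 1.33
- r = 0.7: 0.60/0.51 = 1.18

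At the planned 30 per arm, a one-standard-error chance imbalance at baseline is sqrt(2/30) = 0.26 SD. It shifts the change-score difference by (1-r) × 0.26 SD, which is 0.13 SD at r = 0.5.

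**4. Scale and adjustment together.** This is an illustration in which every input is assumed, including right skew. It uses 27 per arm, a lognormal marker, 4,000 simulated trials per setting and two-sided 5% tests. For a lognormal marker, mean/median = exp(s²/2), where s is the log SD. That is 1.38 at s = 0.8, 1.65 at 1.0 and 2.05 at 1.2.

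| Log SD, true ratio, correlation | Raw change t-test, no common fall | Raw change t-test, levels halve in both arms | Log-scale ANCOVA, log baseline |
|---|---|---|---|
| 1.0, 0.6, 0.6 | 25% | 11% | 62% |
| 1.2, 0.5, 0.5 | 22% | 10% | 66% |
| 1.0, 0.5, 0.5 | 34% | 15% | 81% |
| 0.8, 0.6, 0.5 | 37% | 15% | 75% |

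Repeat runs move these by a point or so, giving ranges of about 21-38%, 10-15% and 62-82%. A fall common to both arms shrinks the raw difference between arms but leaves the spread due to baseline. On the log scale it is a constant shift and does not matter.

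**5. Sensitivity to skew.** At 30 per arm, with a 40% reduction, correlation 0.3-0.7 and no common fall:

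| Log SD | Raw change t-test | Log-scale ANCOVA |
|---|---|---|
| 0.5 | 74-96% | 98-100% |
| 0.8 | 33-57% | 71-92% |
| 1.0 | 19-33% | 52-77% |
| 1.2 | 12-21% | 38-62% |

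The ordering is the same throughout, but the gap is much smaller for a mildly skewed marker.

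**The case against.** Several points on the other side stand.

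- **The protocol's own biomarker section is descriptive.** The commitment to compare arms rests on one general sentence in 11.1 about biochemical endpoints. That term reasonably covers ferritin, D-dimer, CRP, procalcitonin and cytokines, and the wording is firm. The mismatch remains.
- **A reader might infer that the SAP abandons a promised transformation and a promised baseline adjustment.** The text does not go that far. Transformation "may be employed to derive the summary statistics", so it is permitted and not required; only the normality check is firm. Baseline adjustment is implied by naming ANCOVA but is never spelled out.
- **A reader might take 10-15% as the power of the SAP's analysis.** The SAP plans no test on biomarker change. That range also needs levels to halve in both arms, which the documents neither state nor support.
- **A reader might say the tables will be dominated by outliers.** That applies to the means. SAP 8.1 also reports median and IQR, which partly protects the description. Right skew is itself an assumption here, although the protocol's normality check anticipates non-normal data.
- **A reader might infer that the proof-of-concept conclusion is at risk.** It is not. Biomarker change is exploratory, and the protocol ties proof of concept to the Day 14 clinical endpoint.
- **Deferral past database lock does not mean nothing is reported.** The four local markers appear in the safety laboratory tables regardless. The deferral does leave open the pharmacodynamic analysis and the choice of cytokines.

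**Conclusion.** The point holds as an undeclared difference between protocol and SAP for an exploratory endpoint. The between-arm comparison and the normality check are missing from the SAP's biomarker analysis, and SAP 13 does not say so. The marker list is also left open until after lock. These findings are textual and rest on no assumption.

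The size of the loss cannot be derived from the documents. Under the assumed inputs, log-scale ANCOVA detects the effect in about 62-82% of trials. An informal reading of raw mean change, represented by a t-test, does so in about 21-38%, or 10-15% with a common halving. The direction held in every setting tried; the magnitude depends on skew, correlation and the placebo course. This should be corrected, but no primary result depends on it.

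**What to change.** In SAP 12.9.4, for Part 1:

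1. Fix the marker list before unblinding: ferritin, D-dimer, CRP and procalcitonin, plus any central-laboratory cytokines to be assayed. Delete the sentence deferring the decision until after database lock, here and in 12.10.5.
2. Keep the protocol's graphical and Shapiro-Wilk check. Where a marker is skewed, analyse log(value) at Days 3, 7, 14, 28 and 60 by MMRM with treatment, visit, treatment-by-visit, log baseline and log baseline-by-visit.
3. Report the geometric mean ratio (rhu-pGSN/placebo) with 95% CI at each visit, labelled exploratory. Add geometric mean and CV% to the summaries, as 8.1 already does for PK.
4. Leave pGSN out of this model. It is the administered protein, and its Day 3 sample is the 24-hour post-dose PK sample (Protocol Table 5, footnote k), so an arm ratio would largely reflect exposure.

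The log-scale model and geometric mean ratios go beyond what the protocol spells out; they are one sound way to meet 11.1. If the sponsor prefers description only, SAP 13 should declare that and give the reason.

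The cost is a few tables. Samples are already scheduled, and the WHO-score MMRM code in 12.9.2.1.3 has the same structure. The downside is more exploratory estimates without multiplicity control.
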